8.1 Assessment of Adverse Event Severity and Relationship to Treatment

Based on our experience implementing BSFT, we have identified common AEs and SAEs for this population; these will be reported during protocol. The events are defined in Table 2.

Table 2. Family Participants

Adverse Events

1. Arrest
2. Runaway
3. Kicked out of Home
4. School Suspension/Expulsion/Dropout
5. Violence (Victim/Exposure)

Serious Adverse Events

6. Physical/Sexual Abuse
7. Suicidal Behavior
8. Homicidal Behavior
9. Hospitalization (psychiatric, drug related)
10. Death

Unexpected Adverse event 11. Other (indicate if serious)

Adverse events for this study may be identified during regularly scheduled intervals or may be reported at any other times during the study. For adolescents and their parent /guardians that are participating in assessments, the ten adverse events listed above (see Table 2) will be queried specifically at T4,T8,T12 time points. An “other” category has been included to allow sites to capture unexpected adverse events reported by participants which do not fall within the scope of any of the ten defined AEs/SAEs for this protocol. All 13 assessments conducted by the blind research assistant are opportunities for identifying adverse events if reported by the participant. All research assistants conducting primary and/or secondary outcome assessments, will be trained to identify AEs and SAEs at each of these time points. Additionally, anytime during the study, a participant or his/her family member may report an AE. These events will be identified, classified as serious or not, and notified by the therapists or RA- blind to the RA –non blind and will be handled in the same manner like AEs during the formal assessments. In the event that any other person reports an adverse event for the adolescent, the research team must find out with the legal guardian or the adolescent about the occurrence of the event.

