Both, TAU and BSFT therapists will be trained to identify adverse events, and categorize serious adverse events, based on direct reporting during sessions. Upon identification of an adverse event, all research team (blind RA, non-blind RA, and therapists) should categorize the event for seriousness to guarantee that appropriate care and reporting occurs within approximately 24 hours. As soon as any adverse event is identified, either by querying or direct report, the event will be recorded in the AE CRF by the non-blind research assistant. In addition, the Clinical Supervisor at the site will be notified of any and all AEs. All non-serious AEs will be handled based on standardized operation procedures at the site. In both treatment conditions, action may be taken by the therapist to respond to

non-serious events (e.g., booster sessions, or increase in the frequency of sessions). If therapists or blind research assistant were the ones to identify the events, after notifying the Clinical Supervisor, they are to notify and inform the non-blind research assistant, who is then responsible for conducting further evaluations and completion of the AE CRF. All non-serious adverse events require no further reporting. All AE CRFs will be reviewed by the CTP PI weekly to evaluate relatedness to the intervention and resolution.

If the event is categorized as serious, the reporting procedures for SAEs experienced by any participant in the BSFT trial will be in accordance with the CTN Medical Safety Monitoring Policy. In the occurrence of a SAE, the Clinical Supervisor and the CTP PI must be notified when possible within 2 hours of identification. The non-blind research assistant will be responsible for recording the event in the AE CRF. The Clinical Supervisor will be responsible for ensuring care of participants, based on standardized operating procedures at the site. The CTP PI will then be responsible for assessing the event's "relatedness to the intervention".

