8.3 Serious Adverse Events

SAEs include 1) Physical/Sexual Abuse, 2), Suicidal Behavior, 3) Homicidal Behavior, 4) Hospitalization (psychiatric or drug related), and 5) Death.

All of these problems may involve imminent danger to self or other. In cases of current suicidal, homicidal, and abusive behaviors, participants in both BSFT and TAU will be immediately referred to the clinical supervisor to ensure that appropriate crisis intervention services are provided. Each of the CTPs that have expressed interest in this protocol has a procedure in place for managing these emergencies. Serious adverse events listed in this study will also be reported for any family participant. However, these cases will not be withdrawn from the study. Adequate medical care of family members, like with the adolescents, will be provided following the SOPs at each CTP.

1) Physical /Sexual Abuse

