Homicidal behaviors include any attempts to seriously injure or kill another person. Homicidal behaviors also include any ideations (e.g., thoughts/intentions) that are considered to represent a legitimate threat to another person. All homicidal behaviors will be referred to the CTP Clinical Supervisor who will conduct an evaluation to determine the nature of the behaviors, including the legitimacy of the threat. When necessary, the CTP Clinical Supervisor is responsible for notifying the appropriate authorities as well as the potential victim that is identified by a legitimate threat. Adolescent participants with homicidal behaviors will be withdrawn from BSFT. BSFT services may be reinstated when the homicidal behaviors are no longer present. Adolescents and family members will continue to receive study assessments.

4) Hospitalization (psychiatric or drug-related)

Given the chronic nature of drug abuse as well as the high incidence of psychiatric comorbidity among adolescent drug users, we expect that some youth may require hospitalization for psychiatric or drug-related reasons during the protocol. All hospitalizations for psychiatric or drug-related reasons will be reported to the CTP Clinical Supervisor.

When an adolescent is placed in a more restricted environment during the treatment phase of BSFT, therapists will contact the family each month to determine when the adolescent is expected to be released back to live with the family. When appropriate and permitted, family sessions will continue. For adolescents that are released back to live with the family prior to 12-months post-randomization, treatment (in the first 6 months) or “booster” sessions will be conducted with adolescents and family members to facilitate a smooth transition back into the home and to achieve or solidify improvements in family functioning and adolescent behavior problems.

5) Death

For adolescents in BSFT, deaths of primary caregivers and immediate family members (e.g., brother, sisters) that are participating in the intervention will be reported. As with all other SAEs, the CTP Clinical Supervisor is responsible for ensuring that therapists in both conditions follow standard CTP procedures for handling deaths. In BSFT, therapists are expected to conduct sessions with surviving family members to facilitate the family members’ adjustment and to make referrals to appropriate mental health services if necessary.

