8.5 Immediate Report of Serious Adverse Events

Independent of causality, any SAEs that occur during the course of this study must be reported to the Clinical Supervisor and CTP PI when possible within 2 hours of notification. The CTP PI will be responsible for assessing relatedness to the intervention and forwarding the report within 24-hours of identification to the NIDA/CCTN Medical Monitor, the Project Director and Lead Investigator at the University of Miami Center for Family Studies and the Node Study PI. The Lead Investigator is responsible for completing a final written SAE summary report and seeking medical consultation from the BSFT Medical Monitor. Completions and submission of the Summary Report to the NIDA medical office should be done within 2 weeks of notification. The NIDA/CCTN Medical Monitor will then inform the DSMB. The BSFT Project Director will then forward the LI summary report to the Lead Node IRB as well as to other CTPs and Nodes, with a request that they report to all IRBs involved. The CTP PI, the Node Study PI and the Lead Investigator will follow up all SAEs until resolution has been achieved. SAE summary reports will be submitted to NIDA on a quarterly basis.

Reports submitted via telephone or fax to NIDA and to the Lead Investigator and the Protocol Medical Monitor should go to the numbers or electronic addresses listed below.

NIDA Medical Officer	(Voice)	[contact]
	(Fax)	[contact]
[name].:	(Work)	[contact]
BSFT Lead Investigator	(Home)	[contact]
	(Cell)	[contact]
	(Fax)	[contact]
	(Email)	[contact]
[name].:	(Work)	[contact]

[name]

BSFT Co-Lead Investigator/	(Home)	[contact]
Project Director	(Cell)	[contact]
	(Email)	[contact]

[name].:	(Work)	[contact]
BSFT Medical Monitor	(Home)	[contact]
	(Pager)	[contact]
	(Email)	[contact]

Table 2. AEs and SAEs Summary Table

EVENT	IDENTIFICATION By therapists at sessions or RAs blind to condition (B1-T12)	ASSESSMENT PROCEDURES By RA Non-Blind RA (B1, T4, T8, T12)	SERIOUSNESS	CLINICAL ACTION Ensured by the Clinical Supervisor	REPORTING & MONITORING FOR SAFETY Ensured by the CTP PI
1. Arrest	Report	Structured QUESTIONING	NO	Increase frequency/dose of sessions, or booster sessions if therapy completed or other	None
2. Runaway	Report	Structured QUESTIONING	NO	Increase frequency/dose of sessions, or booster sessions if therapy completed or other	None

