For these eight reasons, and, in accordance with the Data Safety Monitoring Board's SOP, presentation of primary and secondary effectiveness outcome data and other data not intended to evaluate safety will be presented for all treatment groups combined, further broken down by study node and by CTP (when more than one CTP per node). No statistical penalty will be taken for these blinded interim analyses of efficacy data that will be conducted for the sole purpose of assessing the acceptability of safety results.

Adverse event data and other data intended for the monitoring of safety will be presented to the DSMB in an unblinded fashion. Because the trial is not powered to demonstrate statistically significant differences in adverse events or other safety outcomes, p-values will not be calculated for any differences observed unless specifically requested by members of the Board to assist in the evaluation of a potential safety concern. No adjustments will be made to the efficacy analyses for the number of interim safety analyses in the final report.

Although an interim analysis of effectiveness data is not planned, the DSMB may feel that such analysis is necessary to permit proper evaluation of safety data. Should an unscheduled interim analysis of efficacy be necessary, the Board will specify the question, the analysis required, the critical

[name]

values for a decision and the statistical procedures necessary to control the overall type 1 error at $p < 0.05$. A protocol amendment will be included in the DSMB report of the analysis describing necessary changes in the statistical plan that result from the analysis.

Should the DSMB desire that an interim analysis plan be established prior to implementation of the trial, we would recommend a single interim analysis to take place after both 1) $\frac{1}{2}$ of the subjects have completed the 8 month follow-up and 2) at least 5 sites from have enrolled some number of subjects (to ensure stability in the estimates of treatment effect variability). The trial will enroll sites “waves.”

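### The Death paragraph of Protocol 8.3 words family-death reporting for BSFT and for members in the intervention, against the arm-neutral SAE rule that opens the same section

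*Protocol*

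**What the plan says.** Section 8.3 lists the SAEs, ending with "4) Hospitalization (psychiatric or drug related), and 5) Death", and then sets a general rule: "Serious adverse events listed in this study will also be reported for any family participant". That rule is limited neither by arm nor by attendance at therapy.

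The paragraph on Death later in 8.3 says: "For adolescents in BSFT, deaths of primary caregivers and immediate family members (e.g., brother, sisters) that are participating in the intervention will be reported". There is no matching sentence for TAU. The next sentence does name both arms, but it concerns what staff do after a death, not whether the death is reported: "the CTP Clinical Supervisor is responsible for ensuring that therapists in both conditions follow standard CTP procedures for handling deaths".

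The other reporting rules are also arm-neutral. Section 8.1 states that "the reporting procedures for SAEs experienced by any participant in the BSFT trial will be in accordance with the CTN Medical Safety Monitoring Policy". Section 8.5 states: "Independent of causality, any SAEs that occur during the course of this study must be reported to the Clinical Supervisor and CTP PI". The summary table in 8.5 classes Death as serious and reportable within 24 hours, with no arm named in its reporting column.

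On use of the data, section 13.0 says: "Adverse event data and other data intended for the monitoring of safety will be presented to the DSMB in an unblinded fashion".

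**The concern.** Section 8.3 gives two reporting scopes for the same event. Staff are likely to consult the narrower one: section 8.2 points forward to the event paragraphs for how each SAE is tracked and resolved, and the Death paragraph is the only one in 8.3 devoted to that event.

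At stake is whether SAE counts can be compared between arms. Section 13.0 says that p-values for safety differences will not be calculated unless the Board asks, so the Board will mostly be reading counts. Where counts are small, a reporting scope that depends on arm can produce an apparent imbalance. If the narrow sentence were followed, the extra events would appear in BSFT.

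**Working it through.** No formula or stated figure is involved, so the check is a comparison of texts.

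**Scope of each rule**

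| Place in the Protocol | Arms | Persons |
|---|---|---|
| 8.1, reporting procedure | both | any trial participant |
| 8.1, scheduled query of the ten events | both | adolescents and assessed parents/guardians |
| 8.3, opening | both | any family participant |
| 8.3, Death | BSFT named, TAU not | caregivers and immediate family taking part in the intervention |
| 8.5, text and summary table | both | any SAE in the study |

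The Death paragraph is the only row that names one arm and the only one that depends on taking part in the intervention.

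**What each rule in 8.3 does with a family death**

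| Who dies | Opening of 8.3 | Death paragraph, read literally |
|---|---|---|
| BSFT caregiver, assessed and attending sessions | reported | reported |
| BSFT caregiver, assessed but not attending | reported | not covered |
| TAU caregiver, assessed | reported | not covered |
| BSFT sibling consented for sessions | reported | reported |
| TAU sibling consented to take part | reported | not covered |

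The second row can occur because section 7.6 puts the primary caregiver into the formal assessments without requiring attendance at therapy. It shows a conflict even within BSFT, so deleting the arm qualifier alone would not be enough. TAU may consist of individual or group therapy (sections 5.1 and 5.2.2). A TAU caregiver might therefore never count as participating in the intervention, even if both arms were named.

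**Number of caregivers.** Section 10.4.2 gives 30 participants per group in a site of 60, and section 3.0 gives 8 sites: 8 × 30 = 240 adolescents per arm. With one assessed primary caregiver each, that is about 240 per arm. One unreported death changes an arm's caregiver proportion by 1/240 = 0.42 percentage points. The protocol gives no expected number of such deaths, so no total can be worked out.

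**Pool of relatives.** Section 7.6 says that BSFT therapists consent further relatives who join sessions, and it states no TAU counterpart. Even under the opening rule, the number of family participants at risk of a reportable event may be larger in BSFT.

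**The case against.** The strongest defence is that the Death paragraph never says TAU deaths go unreported. It can be read as additive: it spells out a group that arises mainly in BSFT, namely relatives brought into sessions, and leaves the general rule intact. Several arm-neutral provisions would already capture a TAU caregiver's death. Besides those quoted above, section 8.1 provides that "For adolescents and their parent /guardians that are participating in assessments, the ten adverse events listed above (see Table 2) will be queried specifically", and it trains therapists in both arms to identify events. Each SAE also gets a relatedness assessment and a written summary, so a relative's death would reach reviewers with its context. Section 13.0 describes no formal comparison of family-death counts.

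Most of this stands. A reader might infer that TAU family deaths are counted as zero, or that BSFT is made to look worse by construction. The documents do not support either reading, because a TAU site would have to set aside every other reporting rule. Nor does anything show that a one-arm rule was intended; this is an inconsistency of wording.

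The argument about the pool of relatives is also only partly a fault of the plan. More relatives in sessions is inherent in comparing family therapy with TAU. TAU may include non-manualized family therapy, and section 3.1 has additional family members consented in general terms. A larger BSFT pool is likely, not certain.

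The defence does not remove the conflict. The additive reading gives the arm qualifier a purpose, but it does not explain why an assessed caregiver outside the sessions falls outside the Death paragraph. Sites are still left to choose between two scopes.

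**Conclusion.** The conflict is real and worth correcting. The Death paragraph is narrower than the opening of 8.3, and than 8.1 and 8.5, both by arm and by participation in the intervention. Capture would differ between arms only where a site applies that paragraph literally. The number of events affected is unknown; I assume it is small. The consequence is confined to SAE ascertainment and the unblinded safety display. The adolescent's own death is covered by the general rules in both arms, and the efficacy analyses and sample size are unaffected.

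A reader might go further and ask for every immediate relative's death to be reported whether or not that person takes part in the study. That exceeds what the documents support: the opening rule is limited to family participants, and section 4.3 requires consent from anyone taking part in any aspect of the study.

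**What to change.** Reconcile the Death paragraph with the opening of 8.3 and with 8.5:

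- Open the sentence with *For adolescents in both conditions*.
- Replace the condition on taking part in the intervention with the scope of the opening rule: any consented family participant, including the assessed primary caregiver whether or not that person attends sessions.
- In safety reports to the DSMB, show family-member SAEs by arm for the assessed primary caregiver as well as for all family participants. The caregiver set is common to both arms and does not grow with session attendance. Section 7.6 allows the caregiver to change during follow-up, so the display should state which caregiver it counts.

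The cost is one reworded sentence, one extra line in the safety display and possibly a few more reports from TAU families.

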8.4 Unexpected events

The eleventh category (“other”) has been included to allow sites to capture unexpected adverse events reported by participants which do not fall within the scope of any of the ten defined AEs/SAEs for this protocol. Any other adverse event serious or non serious for which the specificity is not consistent with the described events in the protocol should be considered under this category. It is up to the judgment of the CTP PI to determine which unexpected events qualify under this category.

8.5 Immediate Report of Serious Adverse Events

Independent of causality, any SAEs that occur during the course of this study must be reported to the Clinical Supervisor and CTP PI when possible within 2 hours of notification. The CTP PI will be responsible for assessing relatedness to the intervention and forwarding the report within 24-hours of identification to the NIDA/CCTN Medical Monitor, the Project Director and Lead Investigator at the University of Miami Center for Family Studies and the Node Study PI. The Lead Investigator is responsible for completing a final written SAE summary report and seeking medical consultation from the BSFT Medical Monitor. Completions and submission of the Summary Report to the NIDA medical office should be done within 2 weeks of notification. The NIDA/CCTN Medical Monitor will then inform the DSMB. The BSFT Project Director will then forward the LI summary report to the Lead Node IRB as well as to other CTPs and Nodes, with a request that they report to all IRBs involved. The CTP PI, the Node Study PI and the Lead Investigator will follow up all SAEs until resolution has been achieved. SAE summary reports will be submitted to NIDA on a quarterly basis.

Reports submitted via telephone or fax to NIDA and to the Lead Investigator and the Protocol Medical Monitor should go to the numbers or electronic addresses listed below.

NIDA Medical Officer	(Voice)	[contact]
	(Fax)	[contact]
[name].:	(Work)	[contact]
BSFT Lead Investigator	(Home)	[contact]
	(Cell)	[contact]
	(Fax)	[contact]
	(Email)	[contact]
[name].:	(Work)	[contact]

[name]

BSFT Co-Lead Investigator/	(Home)	[contact]
Project Director	(Cell)	[contact]
	(Email)	[contact]

[name].:	(Work)	[contact]
BSFT Medical Monitor	(Home)	[contact]
	(Pager)	[contact]
	(Email)	[contact]

Table 2. AEs and SAEs Summary Table

EVENT	IDENTIFICATION By therapists at sessions or RAs blind to condition (B1-T12)	ASSESSMENT PROCEDURES By RA Non-Blind RA (B1, T4, T8, T12)	SERIOUSNESS	CLINICAL ACTION Ensured by the Clinical Supervisor	REPORTING & MONITORING FOR SAFETY Ensured by the CTP PI
1. Arrest	Report	Structured QUESTIONING	NO	Increase frequency/dose of sessions, or booster sessions if therapy completed or other	None
2. Runaway	Report	Structured QUESTIONING	NO	Increase frequency/dose of sessions, or booster sessions if therapy completed or other	None
3. Kicked out of Home	Report	Structured QUESTIONING	NO	Increase frequency/dose of sessions, or booster sessions if therapy completed or other	None
4. School Suspension/Expulsion/Dropout	Report	Structured QUESTIONING	NO	Increase frequency/dose of sessions, or booster sessions if therapy completed or other	None
5. Violence (Victim/Exposure)	Report	Structured QUESTIONING	NO	Increase frequency/dose of sessions, or booster sessions if therapy completed or other	None
6. Physical/Sexual Abuse by family member	Report	Structured QUESTIONING	YES	Mandatory reporting to authority; Increase frequency/dose of sessions, or booster sessions if therapy completed or other	Report to LI and NIDA within 24 hrs
7. Suicidal Behavior	Report	Structured QUESTIONING	YES	Referral to psychiatrist or other	Report to LI and NIDA within 24 hrs
8. Homicidal Behavior	Report	Structured QUESTIONING	YES	Report to police, inform the victim. Referral to a psychiatrist or other. Withdrawal from the intervention	Report to LI and NIDA within 24 hrs
9. Hospitalization (psychiatric, drug related)	Report	Structured QUESTIONING	YES	None or other	Report to LI and NIDA within 24 hrs
10. Death	Report	Structured QUESTIONING	YES	Intensify work with Family in BSFT or other	Report to LI and NIDA within 24 hrs

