5.3.1 Training and Supervision

BSFT: Procedures for training and supervision in the clinical aspects of BSFT are described in detail in Appendix C (and will be provided by the Florida Node RRTC). Training occurs over a 5-month period and involves approximately 144 hours of training and supervision, which include didactic presentations, live supervision, case review and planning, pilot cases and weekly supervision.

Therapists will complete the *Views of Adolescent Drug Abuse Q-Sort (VADAQ)*. The Q-sort is a 56-item questionnaire developed in a collaboration the LI team and the University of Arizona team which is part of the San Francisco-Arizona Node. Therapists will be asked to sort 56 statements of opinion concerning the nature and treatment of adolescent drug abuse (each typed on a separate card) into eight different categories ranging from "least agree: (category 1)

to "most agree" (category 8). This measure will be administered during the therapists selection process, prior randomization to BSFT or TAU. For BSFT therapists only the VADAQ will be administered again the first time the therapists submit a tape for certification in BSFT.

Three times during the course of their BSFT training, therapists will complete a case formulation exercise in which they respond orally to one written clinical vignette depicting a family with adolescents who use illicit drugs. For each vignette, respondents will be asked (a) "What do you see happening in this family, and why does the youth use drugs?"; (b) "What additional information would you want in order to assess this family?"; and, (c) "What would you propose as a preliminary treatment plan?". Therapists' open-ended responses to these questions will be individually (privately) audio taped. This qualitative information will be used by trainers to gauge how training is progressing. This also allows the trainer to better tailor the training to each therapist's progress.

The overall BSFT training includes approximately 96 hours of training delivered in four 3-day workshops – and 48 hours of supervision that occur in weekly supervision sessions. The first workshop includes an extra day to train the therapists on the clinical forms and the identification of therapist' and family AE/SAEs.

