TAU: No additional clinical training or supervision of TAU therapists will be provided as part of this protocol, except as required for research purposes, such as GRP, Adverse and Serious Adverse Events notification and completion of research-related CRFs if any.

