7.7.11 Adverse Events

- Adverse Events/Serious Adverse Events. A general inquiry method will be employed to identify AEs/SAEs (Jacobson, Goldstein, Dominguez, & Steinbook, 1987; Levine & Schooler, 1986) by the Research Assistants. Scheduled inquiries by the non-blind

research assistant will occur at each B1, T2, T4, T8, and T12. However, identification of AEs/SAEs may occur at any point in the project. Often, AEs/SAEs will be identified by therapists if the participant or family members bring them up in the sessions. The Research Assistant blind to condition and who performs drug use outcomes will also identify SAEs and AEs during the monthly assessments with adolescents. Research assistants and therapists in both conditions will be trained to identify adverse events and serious adverse events as defined in this protocol. All AEs/SAEs will be documented by project staff (research assistants responsible for secondary outcomes and other appropriate site research staff) using the Adverse Events CRF designed for this protocol (see Appendix B).

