8.2 Monitoring Adverse Events

As depicted in Figure 2, AEs may be tracked and identified in three ways: 1) the research assistant will inquire and document the occurrence of the listed events during the assessment at B1, T4, T8, T12; 2) the blind research assistant will identify upon self report at all 13 monthly primary outcome assessment points, and/or 3) the adolescent and/or family may report the listed events during scheduled or unscheduled contacts. If an AE is identified, the adolescent will be referred to the

[name]

research assistant- non blind for further assessment of AEs. The assessment and logging of the AE CRFs will be performed by the research assistant responsible for the secondary outcomes assessments. This is to ensure blindness to condition by the blind research assistant. Likewise, if the therapist identifies the adverse event, the participant will be referred to the non-blind research assistant for further assessment. Therapists (both BSFT and TAU) and research assistants will notify the Clinical Supervisor of all AEs. For SAEs, therapists and research assistants will notify CTP PI and Clinical Supervisor within approximately two hours of identification. For all events identified in either the assessment or through therapy contacts, the non-blind Research Assistant is responsible for completing the AE CRF except for evaluation on severity, relatedness to the intervention and resolution status. The latter are the responsibility of the CTP PI. For SAEs, the CTP PI is responsible for completing the SAE Form and notifying the NIDA representative and the LI within 24 hours (via fax or phone). The LI (or Study MD) will complete an SAE Reporting Form and a summary report for every SAE. SAE Summary Reports must be submitted to NIDA within 2 weeks of notification.

Figure 2: AEs & SAEs Identification, Assessment and Report
Research Assistant- Non Blind (T0, T2, T4, T8, T12)

Note: * Research Assistant blind to condition will be trained to identify AEs in the event they are communicated during drug use assessments by the adolescent. In this event, they will refer the adolescent to the Research Assistant responsible of the assessment of secondary outcomes.

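### Adverse events found in therapy sessions share one record with those from scheduled questioning, and the session route differs by arm, so by-arm safety counts can differ at equal risk

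*Protocol*

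**What the plan says.** **Routes of detection.** The summary table in Protocol section 8.5 gives two columns for every listed event. One is identification, "By therapists at sessions or RAs blind to condition (B1-T12". The other is structured questioning by the non-blind research assistant. Section 7.7.11 expects the session route to matter: "Often, AEs/SAEs will be identified by therapists if the participant or family members bring them up in the sessions".

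**One record.** Section 8.1 says events raised outside the formal assessments "will be handled in the same manner like AEs during the formal assessments". Section 8.2 puts all of them on the same form: "For all events identified in either the assessment or through therapy contacts, the non-blind Research Assistant is responsible for completing the AE CRF". No section separates counts by source.

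**The session route by arm.**
- Section 5.2.1 expects most BSFT sessions to include more than one family member. Section 5.2.2 describes TAU as individual, group and non-manualized family work, and says TAU contact may be more frequent than BSFT contact.
- Section 5.3.1 on BSFT: "The first workshop includes an extra day to train the therapists on the clinical forms and the identification of" AEs and SAEs. A BSFT supervisor also reviews, each week, the contact log and summary for every case and a sample of tape.
- Section 5.3.1 on TAU: "No additional clinical training or supervision of TAU therapists will be provided as part of this protocol". An exception follows for research needs, and that exception names AE and SAE notification.
- Sections 7.7.11 and 8.1 say that therapists in both conditions are trained to identify these events.

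**Who sees the result.** Section 13.0: "Adverse event data and other data intended for the monitoring of safety will be presented to the DSMB in an unblinded fashion". P-values are not calculated unless the Board asks for them.

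**The concern.** A by-arm count of adverse events reflects true risk multiplied by the chance that an event is recorded. Scheduled questioning gives that chance a common basis, because the same ten events are asked about at the same times in both arms. The session route does not. It depends on how often the family is seen, who is in the room, what the therapist has been trained to notice, and who reads the notes afterwards. In this trial those features belong to the treatments being compared.

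This concerns events in the randomized adolescent, not only events in relatives. If the Board sees more arrests, runaways, abuse or suicidal behavior under BSFT, it cannot tell harm from better detection. At a site where TAU contact is more intensive, a real BSFT excess could be hidden. With no p-values by default, the Board works from the raw counts.

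**Working it through.** The protocol gives no adverse event rate, capture rate or safety power, so there is no figure of its own to reproduce. The check has two parts.

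**1. The passages side by side**

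| Feature | BSFT | TAU |
|---|---|---|
| Scheduled questioning at T4, T8, T12 (8.1) | yes | yes |
| Monthly contact with blind assistant (8.1, 8.2) | yes | yes |
| Therapist trained to identify AEs (7.7.11, 8.1) | yes | yes |
| Extra workshop day, partly on AEs (5.3.1) | yes | none stated |
| Weekly supervisor review of logs, summaries, tape (5.3.1) | yes | none added |
| Several family members in most sessions (5.2.1, 5.2.2) | expected | varies |
| Contact frequency (5.2.2) | 12 to 16 sessions plus boosters | may be more frequent |

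The first three rows pull the counts together. The next three tend to raise session detection in BSFT. The last may raise it in TAU. The net sign is not determined.

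**2. Illustration of size**

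Inputs:
- 480 participants (section 3.0), taken as 240 per arm. Equal allocation is assumed.
- Equal true risk of 30% in both arms, at most one event each: assumed.
- *s* = chance that scheduled questioning captures an event, the same in both arms: assumed.
- *c* = chance that sessions surface it, independent of *s*: assumed, and allowed to differ by arm.

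P(recorded) = 1 − (1 − s)(1 − c). Expected count = 240 × 0.30 × P(recorded) = 72 × P(recorded).

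BSFT sessions surface more (c = 0.6 v 0.3):
- s = 0.5: 1 − 0.5×0.4 = 0.80 v 1 − 0.5×0.7 = 0.65; counts 57.6 v 46.8; ratio 1.23
- s = 0.7: 0.88 v 0.79; counts 63.4 v 56.9; ratio 1.11
- s = 0.9: 0.96 v 0.93; counts 69.1 v 67.0; ratio 1.03
- s = 1.0: 72 v 72; ratio 1.00

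TAU sessions surface more (c = 0.4 v 0.6):
- s = 0.5: 0.70 v 0.80; ratio 0.875
- s = 0.7: 0.82 v 0.88; ratio 0.93
- s = 0.9: 0.94 v 0.96; ratio 0.98

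With equal c the ratio is 1.00 at every s. Counting only what scheduled questioning elicits gives 72 × s in each arm (36.0 at s = 0.5, 50.4 at s = 0.7), hence equal expected counts, provided s really is equal.

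The largest gap in context: recorded proportions are 57.6/240 = 0.240 and 46.8/240 = 0.195. The standard error of the difference is √[(0.240×0.760 + 0.195×0.805)/240] ≈ 0.038, so the 0.045 gap is about 1.2 standard errors. If the Board asked for a test, it would reach nominal two-sided 5% in about 22% of trials.

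**3. How the split must be made**

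Suppose events a therapist found first were removed from the scheduled count. If session discovery always came first, the remaining share would be s(1 − c). At s = 0.5 that is 0.5×0.4 = 0.20 v 0.5×0.7 = 0.35, or 14.4 v 25.2 expected events, a ratio of 0.57. Sorting by first source alone can therefore reverse the bias.

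**The case against.** **No analysis is misstated.** The same-handling wording in section 8.1 is about notifying and recording, and section 13.0 does not spell out a pooled table. Tabulation by source could sit in an analysis plan that is not at hand. This is fair as far as tables go. But an analysis plan cannot recover a source that was not recorded, and the protocol does fix the single stream and the unblinded view. The AE form is not shown and may already carry the source; if so, only the table is needed.

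**Training is not one-sided.** A reader might infer from section 5.3.1 that TAU therapists are not trained to identify events. The documents do not support that: the TAU sentence has an exception for AE and SAE notification, and sections 7.7.11 and 8.1 cover both arms. The BSFT day is shared with clinical forms, and the length of TAU training is not given. A difference is likely but not quantified. The weekly BSFT review is described as supervision and adherence work, so its effect on event counts is an inference.

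**Direction.** A reader might infer that BSFT will show more events. More frequent TAU contact can offset or reverse this. The common questioning of adolescent and parent, and the blind assistant's monthly contacts, narrow any gap.

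**Size.** It is tempting to insert the engagement rates of section 1.3.2. The 92.9% v 42.3% pair compares two ways of engaging families into BSFT, judged by intake completion. The 81% v 60% pair comes from another study's control groups and counts intake plus a first session. Neither measures session attendance under BSFT and TAU here.

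**The scheduled count is not clean either.** It is collected by a non-blind assistant, a weakness section 5.4.2 acknowledges for secondary outcomes. It also depends on attendance; section 10.4.1 assumes 28% attrition, and section 10.1.1 plans to check whether attrition differs by arm. This stands, and it is why the scheduled count should accompany the all-source count and not replace it.

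**Conclusion.** The point holds in a limited form. Session-found and questioning-found events go into one record, the session route is not equal by design, and the data reach the DSMB unblinded. By-arm counts therefore mix risk with opportunity to detect. They can differ at equal risk; the documents do not show that they will, which way, or by how much.

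The ratios of 0.875 to 1.23 rest wholly on assumed capture rates and on independence between the two routes. The illustration leaves out the blind assistant's monthly contacts, which would shrink the gap. It vanishes if scheduled questioning captures everything or if session capture is equal.

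The consequence falls on the Board's descriptive by-arm safety review and on later reading of the safety tables. The primary drug use analysis is untouched, and serious events are still assessed one by one. The change is worth making because it is cheap and source must be captured while data are being collected.

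**What to change.** In the by-arm safety presentation under section 13.0:

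1. Keep the all-source count by arm.
2. Beside it, show the count of all events elicited by the scheduled structured questioning of adolescent and caregiver at T4, T8 and T12, including any that a therapist had already found. Give the number of completed assessments per arm as denominator. These three times appear in every version of the inquiry schedule; T2 appears in some sections and not in others.
3. List by source, for each arm, the events known only from sessions, supervision or spontaneous report.

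On the AE form, if it does not already do so, record both the source of first identification and whether scheduled questioning also elicited the event. The first field alone is not enough, for the reason shown in the working.

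Cost: at most two fields and one table. Individual AE and SAE recording and expedited reporting do not change. The like-for-like count omits some events, depends on assessment completion, and comes from a non-blind assistant; the table should carry a note saying so.
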